#### **2.3.1 Risk assessment**

No tissue targets or specific hazards to humans were identified in nonclinical general and reproductive toxicology studies.

Dupilumab has an extensive safety database.

As of 28 March 2022 (data cut-off date), approximately 13 577 subjects were enrolled into the development program for dupilumab and are included in the safety population: 564 as healthy volunteers; 4998 from AD studies (including atopic hand and foot dermatitis); 4195 from asthma studies; 880 from the rhinosinusitis (CRSwNP, CRSsNP, and AFRS) studies; 468 from EoE studies; 275 from the allergy (grass and peanut); 1495 from COPD studies; 309 from PN studies; 311 from the urticaria studies (CSU and CICU); 45 from the BP study; and 37 from the ABPA study.

Based on the available sales figures and World Health Organization defined daily dose of 21.4 mg for parenteral formulations, the cumulative patient exposure in marketed experience could be estimated to be 706 212 patient years from 01 March 2017 through 31 March 2022, including 332 123 patient years during the interval period from 01 April 2021 through 31 March 2022.

Dupilumab has been generally well tolerated in all populations tested in clinical development programs consistent with a positive benefit/risk profile. The adverse drug reactions (ADRs) identified to date for dupilumab include injection site reactions, conjunctivitis (including allergic and bacterial), oral herpes, herpes simplex, blepharitis, dry eye, eye pruritus, keratitis, ulcerative keratitis, eosinophilia, anaphylactic reaction, angioedema, serum sickness and arthralgia. These ADRs were not consistently observed in all indications (see Investigator's Brochure [IB] for greater details). More significant serious allergic reactions were very rare. Importantly, no increased overall infection risk was observed in patients treated with dupilumab.

Systemic hypersensitivity has been established as an important identified risk with dupilumab. As protein therapeutics, all monoclonal antibodies are potentially immunogenic. Rare serious and systemic hypersensitivity reactions have been observed in the dupilumab program including serum sickness/serum sickness-like reaction in the adult AD program and anaphylaxis related to dupilumab in the adult asthma clinical trials.

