### 3 OBJECTIVES AND ENDPOINTS

Table 1 - Objectives and endpoints

Objectives	Endpoints
Primary	

• To assess the effect of dupilumab on sleep

• Change from baseline to Week 12 in sleep disturbance score using the Asthma Sleep Disturbance Questionnaire

Secondary	

• To evaluate the effect of dupilumab on additional participant reported sleep outcomes

• Change from baseline to Week 12 on the number of nocturnal awakenings (Sleep Diary)

• Change from baseline to Week 12 in Patient-Reported Outcomes Measurement Information System (PROMIS) Sleep-Related Impairment 8a scale

• Change from baseline to Week 12 in sleep quality (Sleep Diary)

• Change from baseline to Week 12 in restorative sleep (Sleep Diary)

• Change from baseline to Week 12 in wake after sleep onset (WASO) (Sleep Diary)

• Change from baseline to Week 12 in WASO based on actigraphy data

• Change from baseline to Week 12 in Asthma Daytime Symptom Diary (ADSD) and Asthma Nighttime Symptom Diary (ANSO)

• Change from baseline to Week 12 in prebronchodilator forced expiratory volume (pre-BD FEV1)

• Incidence of treatment-emergent adverse events (TEAEs) and serious adverse events (SAEs) including clinically significant changes in vital signs

• Incidence of adverse events of special interest (AESI)

Tertiary/exploratory	

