### **8.3.6 Adverse event of special interest**

An AESI is an AE (serious or nonserious) of scientific and medical concern specific to the Sponsor's product or program, for which ongoing monitoring and immediate notification by the Investigator to the Sponsor is required. Such events may require further investigation in order to characterize and understand them. Adverse events of special interest may be added, modified or removed during a study by protocol amendment.

For these AESIs, the Sponsor will be informed immediately (ie, within 24 hours), per SAE notification described in [Section 10.3.4](#), even if not fulfilling a seriousness criterion, using the screens in the e-CRF.

- Anaphylactic reactions (see [Section 10.9](#)).
- Systemic hypersensitivity reactions.
- Helminthic infections.
- Keratitis.
- Any severe type of conjunctivitis or blepharitis.
- Clinically symptomatic eosinophilia (or eosinophilia associated with clinical symptoms).
- Significant ALT elevation
  - ALT  $>5 \times$  the ULN in participants with baseline ALT  $\leq 2 \times$  ULN; “Baseline” refers to ALT sampled at baseline visit or, if baseline value is unavailable, to the latest ALT value before the baseline visit,  
or
    - ALT  $>8 \times$  ULN if baseline ALT  $>2 \times$  ULN.
- Pregnancy of a female participant entered in a study as well as pregnancy occurring in a female partner of a male participant entered in a study with IMP.

- Pregnancy occurring in a female participant entered in the clinical trial or in a female partner of a male participant entered in the clinical trial. It will be qualified as an SAE only if it fulfills one of the seriousness criteria (see Appendix 3 [[Section 10.3](#)]).
- In the event of pregnancy in a female participant, IMP should be discontinued.
- Follow-up of the pregnancy in a female participant or in a female partner of a male participant is mandatory until the outcome has been determined (See Appendix 4 [[Section 10.4](#)])
- Symptomatic overdose (serious or nonserious) with IMP/NIMP
  - An overdose (accidental or intentional) with the IMP is an event suspected by the Investigator or spontaneously notified by the participant and defined as at least twice the intended dose during an interval of less than 11 days. The circumstances (ie, accidental or intentional) should be clearly specified in the verbatim and symptoms, if any, entered on separate adverse event forms.

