#### **9.4.5 Other safety analyse(s)**

All safety analyses will be performed on the Safety Population.

The incidence of AEs, TEAEs, SAEs, AE leading to permanent treatment discontinuation, AESI and death will be summarized by treatment group.

Treatment-emergent adverse event (TEAE) incidence tables will be presented by system organ class (SOC) (sorted by internationally agreed order), high-level group term (HLGT), high-level term (HLT) and preferred term (PT), the number (n) and percentage (%) of participants experiencing a TEAE. Multiple occurrences of the same event in the same participant will be counted only once in the tables. The denominator for computation of percentages is the safety population within each treatment group.

Proportion of participants with at least one TEAE, serious TEAE, AESI, and TEAE leading to discontinuation of the study will be tabulated by treatment group. In addition, TEAEs will be described according to maximum intensity and relation to the study drug. Serious AEs and AEs leading to study discontinuation that occur outside the treatment-emergent period will be summarized separately.

AESI definitions and the method to identify AESIs will be specified in the SAP.

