1. Anaphylactic reactions: includes anaphylactic reaction using CMQ name CMQsn00021 and programmatic identification of cases based on occurrence of at least two events meeting the algorithm criteria occurring within 2 consecutive days of each other. The latter cases identified using the algorithm will undergo blinded medical review taking into account the timing of events relative to each other and to IMP administration for final determination of an anaphylactic reaction or not.
2. Systemic hypersensitivity reactions: CMQ name CMQsn00214 and [AE corrective treatment/therapy='Y' or Action taken with IMP='Drug withdrawn' or Action taken with IMP='Drug interrupted'] followed by blinded medical review (documented process) for selection of relevant systemic hypersensitivity events
3. Any severe type of conjunctivitis or blepharitis: Based on the CMQ names CMQ10498 and CMQ10497 with "Severe" ticked in Adverse Events eCRF page.
4. Helminthic infections: Based on CMQ name CMQ10548.
5. Keratitis: Based on CMQ name CMQ10642.
6. Clinically symptomatic eosinophilia: based on CMQ name CMQ10641 followed by blinded medical review (documented process) for selection of relevant eosinophilia events.
7. ALT increase: based on the CMQ names CMQ00029 with the addition of "Is the event an AESI" answered YES on AE eCRF as reported by the investigator.

For AESI Anaphylactic reactions, Clinically symptomatic eosinophilia and Systemic hypersensitivity reactions: blinded medical review will be conducted in order to confirm (or not) AESI status for those AEs identified as AESI using programming rules. Only the AEs confirmed as AESI during the medical review will be presented in the analysis.

#11 The codelist to identify Atopic comorbidities is updated, CMQs CMQ10440, CMQ10539 and CMQ10538 have been replaced by CMQ10799 and CMQ10800 to get more appropriate terms.

#12 In accordance with the general changes made to all Dupi studies, the following changes are made:

1. TEAE period is defined as the time from the first administration of the IMP to the last administration of the IMP + 98 days (instead of 84 days in [Section 9](#) from approved SAP);
2. Concomitant medication is defined as any treatments received concomitantly to the IMP, starting from the date of first IMP administration to the date of last administration + 98 days (instead of 14 days in [Section 7.1.2](#) from approved SAP).

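### Addendum #10 leaves untreated systemic hypersensitivity with no action on IMP out of the AESI endpoint, even when the investigator reported it as an AESI

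*SAP*

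**What the plan says.** AESI incidence is a secondary safety endpoint (Protocol Section 3, Table 1). Protocol 2.3.1 states: "Systemic hypersensitivity has been established as an important identified risk with dupilumab".

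Protocol 8.3.6 defines an AESI as an event for which "ongoing monitoring and immediate notification by the Investigator to the Sponsor is required". Its list includes "Systemic hypersensitivity reactions" with nothing further attached. The sponsor must be told within 24 hours, "even if not fulfilling a seriousness criterion, using the screens in the e-CRF". SAP 9.1.7 repeats the unqualified category. Table 15-2 of the approved SAP finds these events with the narrow Hypersensitivity SMQ alone.

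Addendum #10, item 2, replaces that search with "Systemic hypersensitivity reactions: CMQ name CMQsn00214 and [AE corrective treatment/therapy='Y' or Action taken with IMP='Drug withdrawn' or Action taken with IMP='Drug interrupted". The selected events then go to blinded medical review. The closing paragraph of #10 confines the review to events already picked out by the programmed rules, and adds: "Only the AEs confirmed as AESI during the medical review will be presented in the analysis".

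Item 7 of #10 (ALT increase) shows that the AE eCRF asks the investigator whether the event is an AESI. Item 2 does not use that answer.

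Protocol 9.4.5 states: "AESI definitions and the method to identify AESIs will be specified in the SAP".

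**The concern.** The treatment-or-action condition comes before the review and must be met. The reviewers can remove events but cannot bring back one that the program did not select. An investigator can therefore judge an event to be a systemic hypersensitivity reaction and notify it as an AESI, and it will still be absent from the AESI table if it resolved without treatment and IMP was left alone.

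What is at stake is the meaning of a secondary safety endpoint for an important identified risk. A reader of the AESI table, with Protocol 8.3.6 or SAP 9.1.7 in hand, would take the row to be all systemic hypersensitivity reactions. It would in fact be those that were treated or that led to action on IMP. The same rule feeds the overview rows for TEAEs of special interest in SAP 9.1. Addendum #10 gives no reason for the narrowing and does not amend 9.1.7.

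**Working it through.** The plan gives no figure to reproduce here, so the check is mainly one of logic.

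**Step 1: definitions side by side.**
- Protocol 8.3.6: category named, no condition.
- SAP 9.1.7: same category, no condition.
- SAP Table 15-2: narrow SMQ, no further condition.
- Addendum #10, item 2: CMQ match AND (corrective treatment OR IMP withdrawn OR IMP interrupted), then blinded review.
- Addendum #10, item 6 (symptomatic eosinophilia), for comparison: CMQ match, then blinded review, with no treatment or action condition.

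**Step 2: apply item 2 to an event that matches CMQsn00214 and that the investigator reported as an AESI.**
- Treated, on any day, during dosing or follow-up: goes to review.
- Untreated, and the reaction leads to withdrawal or interruption of IMP: goes to review.
- Untreated during dosing, IMP continued: not reviewed, not counted.
- Untreated after the final planned dose: not reviewed unless an IMP action is recorded. No dose then remains to withdraw or interrupt, so this is likely not counted. That is an inference, because the documents do not describe how the IMP-action field is completed once dosing has ended.

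Protocol 7.1.2 points the same way late in dosing. Its working definition of an investigator-decided temporary discontinuation is more than one dose not given, so at least two doses must still be due. Whether the eCRF field follows that definition is not stated.

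**Step 3: how much calendar time lies after the final dose.** Share = tail ÷ (days from first to last dose + tail). SAP 3.3 describes dosing every two weeks until Week 12. The range below takes the last dose at Day 85 (84 days after Day 1) or at Day 71 (70 days after). The tail is 84 days (follow-up of up to 12 weeks, and SAP Section 9) or 98 days (Addendum #12).
- Day 85, 84-day tail: 84 ÷ (84 + 84) = 84/168 = 50.0%
- Day 85, 98-day tail: 98 ÷ (84 + 98) = 98/182 = 53.8%
- Day 71, 84-day tail: 84 ÷ (70 + 84) = 84/154 = 54.5%
- Day 71, 98-day tail: 98 ÷ (70 + 98) = 98/168 = 58.3%

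These are shares of time for a participant dosed to the end and followed for the full tail. They are not shares of events. The 98-day tail runs 14 days past the planned follow-up (98 − 84), and follow-up stops sooner on a switch to commercial dupilumab or another biologic.

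**Step 4: number of events affected.** Not computable. The documents give no event counts, no proportion treated and no distribution of onset times.

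**The case against.** The best defence is that Protocol 9.4.5 hands both AESI definitions and the identification method to the SAP, so the sponsor may set an algorithm. That stands: this is a narrowing that has not been reconciled with SAP 9.1.7, not a protocol breach. Notification within 24 hours and follow-up of AESIs are untouched.

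It is also true that the excluded events do not vanish. They remain in the TEAE tables by preferred term, relationship and severity (SAP 9.1.1 to 9.1.3) and in the AE listings. Serious ones are in the SAE tables (9.1.4). Some may count as anaphylaxis under item 1, which has no treatment or action condition.

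Several stronger readings are tempting and are not supported:
- *That investigator-reported AESIs are lost after the last dose.* The three conditions are alternatives, so a treated event qualifies on any day. A reaction that itself leads to withdrawal also follows the last dose given, and it qualifies. The loss is confined to untreated events with no IMP action, and it occurs during dosing too.
- *That about half of the events are lost.* The 50% to 58% above is calendar time only.
- *That the rule favours dupilumab.* It is the same in both arms and the review is blinded. The direction of any bias cannot be determined.
- *That the condition serves no purpose and should go.* The approved search had no criterion for systemic and no review. Some marker may help specificity, and Protocol 7.1.1 itself uses need for treatment in its discontinuation criterion for allergic reactions. The terms in CMQsn00214 are not shown, so this cannot be settled here.
- *That the other AESI rules share the fault.* No such defect has been shown.

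**Conclusion.** The concern holds in a limited form. Item 2 makes the tabulated category narrower than the one in Protocol 8.3.6, SAP 9.1.7 and SAP Table 15-2. It shuts out of the blinded review any systemic hypersensitivity event with no corrective treatment and no action on IMP, whatever the investigator reported. This follows from the text and needs no assumption.

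That corrective treatment is effectively the only route after the final planned dose is a reasonable inference that depends on undocumented eCRF coding. The effect on the AESI count can only be downward within this category; its size and any imbalance between arms are unknown. With the events still visible elsewhere, this is an inexpensive improvement to the agreement between definition and table, not a threat to the safety evaluation as a whole.

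**What to change.** - Reword Addendum #10, item 2, so that an event enters blinded review if it matches CMQsn00214 and meets the treatment-or-action condition, OR the investigator flagged it on the AE eCRF as a systemic hypersensitivity AESI. The documents show that the form asks whether an event is an AESI, but not whether it records which category. If it does not, state how the category is assigned.
- Add one row per arm for investigator-reported systemic hypersensitivity AESIs not confirmed by the review, with reasons.
- Align SAP 9.1.7 with the rule, so that the reader knows what the tabulated category contains.

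The change should be made while the review is still blinded. The cost is a few sentences, a few more events for the reviewers and one table row. The drawback is a slight departure from the current algorithm, whose count can still be shown as a second row.

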### Duration of study period (per participant):

Study duration per participant will be approximately 16 weeks and up to 29 weeks.

The study includes 3 study periods:

- **Screening period:**
  - Screening Period 1: Day -35 to Day -12, from signed informed consent.
  - Screening Period 2 (Pre-baseline assessments): participants eligible to continue will complete the assessments specified in the schedule of activities (SoA) from Day -11 to Day -1 (right before Day 1).
  - If preferred by the participant and the investigator for logistic reasons, screening visit 1 (SV1) and screening visit 2 (SV2) can be merged into a single on-site visit.  
Importantly, this single screening visit will have to be done on Day -11 at the latest.
- Randomized, placebo-controlled **treatment period:** 12 weeks from baseline (Day 1).
- Post-treatment **follow-up period:** up to 12 weeks or until the participant switches to commercialized dupilumab (or other biologic product), whichever comes first.

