## 9.5 INTERIM ANALYSES

An interim analysis (IA) in the study is planned for the purpose of [REDACTED] when approximately 50% of participants (approximately 130 participants from the ITTp population) would have completed Week 12 visit or discontinued the study. The sample size re-estimation is planned to mitigate risk of power loss, given the large variability of placebo effects observed in [REDACTED] [REDACTED] Interim analysis will be performed as follows:

- The sample size re-estimation will be performed based on the observed treatment effects at the time of IA. Sample size may be increased if conditional power falls into the promising zone. No additional IA will be performed in the case of sample size increase. The test statistic at the final analysis may be adjusted as appropriate and details will be specified in the SAP.
- There is no plan to stop trial early for superiority at the time of IA. In order to preserve the overall Type I error rate of 0.05 (2-sided), gamma family alpha spending function will be utilized.

The IA will be performed by an internal independent statistical team, who are separate from personnel involved in the trial conduct. An independent Interim Analysis Committee (IAC) consisting of two clinicians and one statistician will review the results and make decision if the sample size needs to be adjusted based on prespecified criteria. A detailed plan will be defined in the SAP, including the plan to describe the processes intended to control access to comparative interim results to preserve trial integrity. People involved in the conduct of the study (participants, Investigators, Study Team, and Project Team) will have no access to the IA results.

At the time of IA, the primary efficacy endpoint will be analyzed using the same method described in the primary endpoint section ([Section 9.4.2](#)). The analysis population for the IA will be approximately 130 randomized participants from the ITTp population. The analysis of the endpoints will use all the data collected for the analysis population up to the IA cut-off time.

The database lock for final analysis is planned based on the date when the last participant completes the Week 12 visit or discontinues from the study before Week 12. Analyses will be based on all data collected up to this database lock and will be considered as the final analysis in the CSR.

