7.1.3. Post-treatment medications

Post-treatment medications are those the participant took (continued or initiated) in the period running from the 15th day after the last administration of IMP up to the end of the study, based on Investigator's decision. Post-treatment medications will not be summarized or presented in the CSR.

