8.2.13. Multiplicity issues

In order to handle multiple primary or secondary endpoints, the overall Type-I error will be controlled by the use of a hierarchical inferential approach:

- Statistical significance of the primary analysis at the 0.05 alpha level will be required before drawing inferential conclusions about first secondary endpoint
- Inferential conclusions about successive secondary endpoints will require statistical significance of the prior one.

Hierarchical testing will be performed in the same order as described below:

1. Change from Baseline to Week 12 in the Asthma Sleep Disturbance Questionnaire (primary endpoint)
2. Change from Baseline to Week 12 in the average number of nocturnal awakenings (first secondary endpoint)
3. Change from Baseline to Week 12 in PROMIS t-score

This fixed hierarchical approach will ensure a strong control of the overall Type-I error rate at the 0.05 level.

Additional endpoints (secondary or tertiary) that are not included in the hierarchical testing procedure will not be formally tested (i.e., nominal p-value provided for descriptive purpose only).

9. Safety Analysis

All safety results will be summarized using the Safety analysis set by actual study intervention group.

The observation periods include:

- The **pre-treatment** period is defined as the time from the signed informed consent date up to first administration of the IMP.
- The **treatment-emergent adverse event** (TEAE) period is defined as the time from the first administration of the IMP (on Day 1) to the last administration of the IMP + 84 days or until the participant switches to commercialized dupilumab or other biologics
- The **post-treatment** period is defined as the time starting 1 day after the end of the TEAE period up to the end of the study follow-up.

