9.1. Adverse Events

The adverse event types include:

- **Pre-treatment adverse events** are adverse events that developed or worsened or became serious during the pre-treatment period.
- **Treatment-emergent adverse events** are adverse events that developed or worsened or became serious during the TEAE period.
- **Post-treatment adverse events** are adverse events that developed or worsened or became serious during the post-treatment period. AEs categorized as post-treatment AEs (following the rules specified below) will not be summarized.

The primary focus of AE reporting will be on TEAEs. Pre-treatment adverse events will be summarized separately.

All AEs will be coded to a LLT, PT, HLT, HLG, and associated primary SOC using the version of Medical Dictionary for Regulatory Activities (MedDRA) currently in effect at Sanofi at the time of each database lock.

Adverse events will be recorded from the time of signed informed consent until the end of the study or the resolution/stabilization of all SAE and AESI.

If an adverse event date/time of onset (occurrence, worsening, or becoming serious) is incomplete, an imputation algorithm will be used to classify the adverse event as pre-treatment, treatment-emergent, or post-treatment. The algorithm for imputing date/time of onset will be conservative and will classify an adverse event as treatment-emergent unless there is definitive information to determine it is pre-treatment or post-treatment. Details on classification of adverse events with missing or partial onset dates are provided in [Section 15.4.4](#).

Adverse events will be summarized by primary SOC, HLG, HLT, and PT, sorted by internationally agreed order of primary SOC and then alphabetically for the other levels, for each study intervention group using number and percentage of participants experiencing an adverse event. Multiple occurrences of the same event in the same participant will be counted only once in the tables within an observation period (pre-treatment period or TEAE period). The denominator for computation of percentages will be the safety analysis set within each study intervention group. Participants experiencing asthma exacerbations will be further summarized using the LLT level as appropriate within adverse event summaries.

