Spirometry (Pre-BD FEV ₁) ^m	X ^l		X	X	X	X	X		
Patient assessments (at home)									
Asthma Sleep Disturbance Questionnaire			←=====daily=====→						Electronic devices; Baseline sleep disturbance scores will be the mean scores recorded for the 7 days prior to randomization.

Procedure	Screening		Intervention Period (weeks) ^a				E/D	Follow-up (up to 12 weeks after last IMP dose) ^b	Notes
	D-35 to D-12	D-11	W0 (D1)	W4 ±3 days	W8 ±3 days	W12 ±3 days			
Sleep Diary		←=====daily=====→							Electronic devices
Actigraphy ^c		X	X	X	X	X	X		Further details on the procedure will be provided in a separate instruction manual
ADSD (Asthma Daytime Symptoms Diary)		X	X	X	X	X	X		Electronic devices: completed by the patient for 7 days prior to the visit, every 4 weeks. The device will be provided to participants at SV2.
ANSD (Asthma Nighttime Symptoms Diary)		X	X	X	X	X	X		Electronic devices: completed by the patient for 7 days including the visit day, every 4 weeks. The device will be provided to participants at SV2.
Patient assessments (at clinic)									
[REDACTED] ^d	X		X	X	X	X	X		Electronic devices
[REDACTED]			X			X			Type II home [REDACTED] devices
[REDACTED]			X	X	X	X	X		Electronic devices
[REDACTED]				X	X	X	X		Electronic devices
PROMIS–Sleep Related Impairment 8a scale on sleep			X	X	X	X	X		Electronic devices
[REDACTED]			X	X	X	X	X		Electronic devices

Procedure	Screening		Intervention Period (weeks) ^a				E/D	Follow-up (up to 12 weeks after last IMP dose) ^b	Notes
	D-35 to D-12	D-11	W0 (D1)	W4 ±3 days	W8 ±3 days	W12 ±3 days			
[REDACTED]			X	X		X	X		Electronic devices
AE, SAE, AESI	←=====→							AE, SAE and AESI will be collected as of SV1	
Prior and concomitant medication review	X	X	X	X	X	X	X		
Device deficiencies			X	X	X	X	X		This refers to prefilled syringes

a In exceptional situations when the participant cannot attend an on-site visit during the intervention period, the visit can be performed remotely ensuring at least the procedures that can be done at home: PROs completion, actigraphy, home [REDACTED] if applicable, IMP administration, blood samples collection, pregnancy test, if applicable, safety reporting, and concomitant medications.

b Post-treatment Follow-up: up to 12 weeks or until the participant switches to commercialized dupilumab (or other biologic product), whatever comes first.

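### The + 98-day concomitant-medication window in SAP Addendum #12 contradicts SAP 7.1.3 and lets steroids taken after Week 12 define a Week 12 subgroup; its + 98-day TEAE window runs past planned follow-up

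*SAP*

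**What the plan says.** **Medication windows.** SAP 7.1.2 defined concomitant medication as running from first dose to last dose + 14 days. Addendum #12 replaces 14 by 98 days, citing general changes across the dupilumab studies. SAP 7.1.3 is not amended. It still places post-treatment medications "in the period running from the 15th day after the last administration of IMP up to the end of the study" and says that they will not be presented. Protocol 6.5 leaves asthma treatment during follow-up to the investigator's judgment.

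**Subgroup.** SAP 8.1.4 repeats the primary analysis by whether participants had concomitant SCS rescue medication. Addendum #4 changes how those drugs are identified (ATC code from the reliever page) but sets no end date.

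**TEAE window.** SAP Section 9 ran the period "to the last administration of the IMP + 84 days or until the participant switches to commercialized dupilumab or other biologics". Addendum #12 now says: "TEAE period is defined as the time from the first administration of the IMP to the last administration of the IMP + 98 days". It gives 98 as a replacement for 84 and does not mention the switch. The protocol synopsis sets follow-up at "up to 12 weeks or until the participant switches to commercialized dupilumab (or other biologic product), whichever comes first". The schedule of activities and SAP 3.1 count those 12 weeks from the last dose. AEs are collected to V6 (Protocol 8.3.1), and for switchers V6 precedes the first injection of the new biologic.

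**AE tables.** SAP 9.1 reports participants with an event: "The denominator for computation of percentages will be the safety analysis set within each study intervention group". Participant-years are planned only for IMP exposure (SAP 7.2.1).

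**The concern.** The medication rules cannot both be programmed. A drug started 30 days after the last dose is concomitant under #12 and tabulated; under 7.1.3 it is post-treatment and not shown. If #12 prevails, the controller and rescue tables combine blinded treatment on stable background therapy with a follow-up period in which therapy may be changed freely. An on-treatment contrast in rescue use is then diluted. The subgroup effect is worse in kind: exposure after the endpoint has been measured could decide which subgroup of the Week 12 analysis a participant joins.

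For adverse events, the nominal window is longer than the time anyone is scheduled to be observed. Observed time after the last dose can range from almost nothing (a switch straight after V5) to 84 days. No planned table shows follow-up or switching by arm, so a reader of the crude percentages could not tell whether the arms were watched for the same time.

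**Working it through.** **1. Planned follow-up.** Inputs: screening from Day -35, 12 weeks of treatment, up to 12 weeks of follow-up (Protocol 4.1).

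- 35 + 84 + 84 = 203 days = 29 weeks, which is the stated maximum study duration.
- Observing a full 98-day window would need 35 + 84 + 98 = 217 days = 31 weeks, 14 days more.
- The 84-day limit depends on the starting point. The synopsis also counts follow-up from the end of the treatment period. On that count a participant last dosed at Week 10 is followed for 84 + 84 - 70 = 98 days.

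**2. Medication windows** (last dose at Week 12, 84 days after first dose).

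| Days after last dose | Approved SAP 7.1.2 | SAP 7.1.3 (unrevised) | Addendum #12 |
|---|---|---|---|
| 0 to 14 | concomitant | not applicable | concomitant |
| 15 to 98 | not concomitant | post-treatment, not shown, up to end of study | concomitant |

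- Window length: 84 + 14 = 98 days before and 84 + 98 = 182 days now; 182/98 = 1.86.
- The conflict covers 98 - 14 = 84 nominal days, of which 84 - 14 = 70 fall inside an 84-day follow-up.

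**3. The subgroup.** The Week 12 score averages the 28 days up to Day 85 (SAP 8 and 15.5). As an illustration, a steroid course on Day 120 falls 120 - 85 = 35 days after a Day 85 last dose. That is inside 98 days and outside 14, so under #12 it classifies the participant although it cannot have affected the score. The + 14-day rule is not exact either. It reaches 14 days past Week 12 for completers, and for a participant who stopped dosing at Week 4 it closes at Week 6, although off-treatment scores to Week 12 are generally used. The subgroup therefore needs its own end date.

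**4. Share of the TEAE window observed.** The nominal window is 84 + 98 = 182 days.

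- Full follow-up: 168/182 = 92.3%.
- Switch right after the last dose: 84/182 = 46.2%. Under the 84-day window it was 84/168 = 50.0%, so most of this gap predates #12.

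**5. Effect on crude percentages.** Assume the same constant rate r of first events per year in both arms, with a share s switching at V5. Write p(d) = 1 - exp(-r × d/365).

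Incidence = s × p(84) + (1 - s) × p(168), so the difference is (s placebo - s dupilumab) × [p(168) - p(84)].

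With assumed s = 0.40 on placebo and 0.20 on dupilumab:

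| r per year | p(84) | p(168) | Placebo | Dupilumab | Difference (unrounded inputs) |
|---|---|---|---|---|---|
| 1 | 20.6% | 36.9% | 30.4% | 33.6% | 3.3 points |
| 2 | 36.9% | 60.2% | 50.9% | 55.5% | 4.7 points |
| 3 | 49.9% | 74.9% | 64.9% | 69.9% | 5.0 points |

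- Rare event, 168-day incidence 5%: p(84) = 1 - √0.95 = 2.5%, and the difference is 0.20 × (5.0 - 2.5) = 0.5 point.
- Equal switching: zero. More switching on dupilumab: the sign reverses.
- The figure 98 does not enter the formula. If no AE is collected after V6, the result is the same for an 84-day or a 98-day window.

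**The case against.** Several points on the other side stand.

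- The extra 14 days apply to both arms and add nothing to a participant denominator. Because post-treatment AEs are not summarised and V6 has no plus-or-minus allowance in the schedule, a longer window keeps events reported at a late V6 in the tables. That is the inclusive choice, and matching other dupilumab studies is a fair reason for it.
- #12 can be read as changing only the number and leaving the switch cut-off in place. A reader might infer that post-switch events will now be counted. Since AE collection ends at V6 and V6 precedes the first biologic injection, few could enter, apart from related SAEs that an investigator later learns of. A clarifying phrase is enough.
- A reader might infer that #12 makes follow-up unequal, or that placebo percentages will be lowered because placebo participants switch sooner. The documents support neither. Unequal follow-up comes from the switch rule in the protocol and the approved SAP. No switching figures are given, and the direction is open: poorly controlled participants may switch, but so may participants doing well who wish to continue.
- A reader might also conclude that the main TEAE tables should stop at last dose + 14 days. Protocol 4.2 rests the 12-week follow-up on a median of 9 weeks to undetectable drug, so that cut would drop much of the relevant exposure. Nor is that window fully observed in someone who switches straight after V5.
- The medication tables carry no between-group test, and the subgroup p-values are nominal. Addendum #9 also stops most drugs started after the end-of-treatment visit from counting as prohibited.

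The last point limits the consequence but does not remove the contradiction with 7.1.3 or the misclassification in the subgroup.

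**Conclusion.** The concern holds in two parts of unequal weight.

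The firm part is medication. #12 and SAP 7.1.3 give opposite instructions from day 15 after the last dose. The concomitant window nearly doubles, from 98 to 182 days with a last dose at Week 12, and steroid use after Week 12 can define a subgroup of the Week 12 primary analysis. This follows from the text and needs no assumption about the data, although the number of participants affected cannot be derived.

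The lesser part is adverse events. The + 98-day window exceeds the longest follow-up by 14 days when follow-up is counted from the last dose, as in the schedule and SAP 3.1, and #12 is silent on the switch cut-off. By itself this does not bias the arm comparison. Crude percentages would be distorted only by differential switching: about 3 to 5 points under the assumed 40% v 20% shares and 1 to 3 events per year, about 0.5 point for a 5% event, and zero with equal switching.

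Two side matters need reconciling but do not carry the point. On the Week 12 lock, Protocol 9.5 says "Analyses will be based on all data collected up to this database lock and will be considered as the final analysis in the CSR", while SAP 3.1 adds a later lock and puts both in the CSR. In the SAP's copy of the schedule, as far as it can be read, the row "Prior and concomitant medication review" has no mark at V6, although Protocol 6.5 asks for medications to be recorded during the study.

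**What to change.** 1. Restore the + 14-day concomitant window, or revise SAP 7.1.3 to match #12. If 98 days is kept, show treatment-period and follow-up use separately.
2. In either case, for the SAP 8.1.4 subgroup count only SCS rescue use from first dose up to the Week 12 assessment.
3. State in #12 that the TEAE period ends at the earliest of last dose + 98 days, V6 or end of study, and start of a biologic.
4. Keep the TEAE percentages. As a supportive display, add follow-up time and switching by arm, and events per 100 participant-years of observed time. If switch dates are not recorded, the V6 date can close the observed time.
5. Reconcile Protocol 9.5 with the two locks in SAP 3.1, and the V6 medication-review entry with Protocol 6.5.

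The cost is a few sentences of addendum wording, one date condition in the subgroup program and one extra table set. Restoring + 14 days would also depart from the convention that #12 cites for the other dupilumab studies; revising 7.1.3 instead avoids that.
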